3.7.5.2 The percent reduction in insulin requirement

Subjects will record their total daily insulin dose on self-monitoring diaries. The insulin requirement will be evaluated at 75±5 days following the initial infusion (and final infusion if applicable). The reduction percentages from the baseline insulin requirement at both times for a subject, if applicable, are calculated accordingly. The analysis of the reduction percentage adopts the method for a continuous variable.

3.7.5.3 HbA1c

HbA1c is measured at 75±5 days following the initial and final infusion (if applicable). The analysis of this measure adopts the method for a continuous scale variable. Data will be displayed as mean, standard deviation, minimum and maximum. In addition, 95% confidence intervals will be computed using an appropriate technique. In addition, change from baseline will be computed. Descriptive statistics and confidence intervals will be computed using the methods used for the original variable.

3.7.5.4 Mean amplitude of glycemic excursions (MAGE)

The MAGE requires capillary glucose readings over two consecutive days (a minimum of four readings a day), and is defined as the arithmetic mean of blood sugar increases (or decreases) when both increases and decreases (or vice-verse) at subsequent points in time are greater than 1 standard deviation of the blood sugar for the same two day period [2]. If the MAGE is ≥ 11.1 mmol/L, the subject is considered to have labile diabetes. The

MAGE will be measured at 75±5 days following the initial and final infusion (if applicable).

The first analysis for this variable directly uses MAGE and adopts the method for a continuous scale variable. Subjects will also be categorized into two groups depending on whether or not the MAGE ≥ 11.1 mmol/L. The analysis of the rate of labile diabetes will be displayed using the methods described for a binary outcome variable.

3.7.5.5 Glycemic lability index

LI is a measure of lability which is based on the change in glucose over time. The LI requires 4 or more daily capillary blood glucose (BG) measurements over a 4 week period. For each week, the sum of the squared differences in consecutive glucose readings is divided by the hours apart the readings are determined. Only differences in time that were greater than or equal to 1 hour and less than or equal to 12 hours are used in calculations. This sum is calculated for each of the four weeks and the LI is the mean of the four weekly values [3], that is:

$$LI = \frac{1}{4} \times \sum_{i=1}^4 \sum_{j=1}^{N_i} \frac{(\Delta Gluc_{i,j})^2}{\Delta h_{i,j}}$$

where $\Delta Gluc_{i,j}$ is the j^{th} eligible difference of glucose readings in the i^{th} week, $\Delta h_{i,j}$ is the time interval in hours for the j^{th} eligible difference of glucose readings in the i^{th} week.

N_i is the total number of the eligible differences of glucose readings in the i^{th} week which may vary from week to week.

Most subjects have scores under 300 mmol/L²/h·wk⁻¹ with a median of 223 (25 – 75th percentiles 130 – 329 mmol/ L²/h·wk⁻¹). An LI ≥ 433 mmol/ L²/h·wk⁻¹ (90th percentile) indicates serious problems with glycemic lability. The LI will be measured at 75 ± 5 days following the initial and final infusion (if applicable). The first analysis for this variable directly uses LI and adopts the method described for continuous scale variables. Change from baseline will also be computed and analyzed using the same methods.

Subjects will also be categorized into two groups depending on whether or not the LI ≥ 433 mmol/ L²/h·wk⁻¹. The analysis of the rate of serious problems with glycemic lability will also be analyzed using the method for binary outcomes.

3.7.5.6 Ryan hypoglycemia severity (HYPO) score

The HYPO score involves subject recording of blood glucose readings and hypoglycemic events (BG < 3.0 mmol/L [54 mg/dL]) over a 4-week period and recall of all severe hypoglycemic episodes in the previous 12 months. The HYPO score is a scalar quantity based on the severity of hypoglycemic events over a four week period. A hypoglycemic event occurs when a blood sugar reading is less than 54 mg/dL and a series of self-reported questionnaire items determine the severity. The HYPO score is the sum of points awarded to each hypoglycemic event, where a large HYPO score indicates more severity [3].

A HYPO score greater than or equal to the 90th percentile (1047) of values derived from an unselected group of type 1 diabetic subjects indicates severe problems with

hypoglycemia. The HYPO score will be measured at 75 ± 5 days following the initial and final infusion (if applicable).

The analysis of the raw HYPO score adopts the method for continuous scale variable. Change from baseline will also be calculated and analyzed using the same method. Subjects with HYPO scores greater than or equal to 1047 will be classified as having severe problems with hypoglycemia, and the analysis of the true rate of this event adopts the method for binary outcome variables.

3.7.5.7 Basal (fasting) and 90-min glucose and C-peptide derived from the mixed-meal tolerance test

The partial graft function of islet transplantation is indicated by continued C-peptide production. Basal and 90-min glucose and C-peptide derived from the MMTT will be measured at 75 ± 5 days following the initial and final infusion (if applicable). The glucose levels (fasting and 90 minute) are continuous variables and will be analyzed using the method for continuous scale variables. Change from basal to 90 minutes will be calculated and analyzed using the same methods. Change from baseline for basal, 90 minutes and the difference between 90 minutes and basal will also be analyzed using the same methods.

3.7.5.8 β -score

The β -score is an assessment of β -cell graft function after islet transplantation and is treated as a continuous variable and ranges from 0 (no graft function) to 8.

The β -score is generated from a composite scoring system based on fasting plasma glucose values (mmol/L), HbA1c(%), daily insulin consumption (units/kg) or oral hypoglycemic agents use, and stimulated C-peptide levels (nmol/L). For each of these measures, scores of 0, 1, and 2 are assigned to abnormal, intermediate, and normal values, respectively. The β -score is then calculated as the sum of the four scores [4].

The β -score will be measured at 75 ± 5 days following the initial and final infusion (if applicable) and will be analyzed using the method for a continuous variable.

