2.3.2.3 Safety endpoints

At 75 ± 5 days following each transplant and 365 ± 14 days following the first and final islet transplant(s):

- The incidence and severity of adverse events (AEs) related to the islet transplant procedure, including: bleeding (>2 g/dL decrease in hemoglobin concentration); segmental portal vein thrombosis; biliary puncture; wound complication (infection or subsequent hernia); and increased transaminase levels >5 times upper limit of normal (ULN)
- The incidence and severity of AEs related to the immunosuppression including: allergy; reduction in glomerular filtration rate (GFR); increase in urinary albumin excretion; addition or intensification of anti-hypertensive therapy; addition or intensification of anti-hyperlipidemic therapy; oral ulcers; lower extremity edema; gastrointestinal toxicity; neutropenia, anemia, or thrombocytopenia; viral, bacterial, or fungal infections; and benign or malignant neoplasms
- The incidence of change in the immunosuppression drug regimen
- The incidence of immune sensitization defined by presence of anti-HLA (histocompatibility antigen) antibodies absent prior to transplantation

At 365 ± 14 days following the first islet transplant:

- The incidence of worsening retinopathy as assessed by change in retinal photography

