3.1 Study Period and Visit Window Definition

3.1.1 Study Period

The trial consists of three periods: (1) the pretransplant period, which includes screening, enrollment, and wait list time; (2) the period that includes the islet transplant procedure(s); and (3) follow-up visits through 24 months following the final transplant. The study period of this trial is a 24-month follow-up after the final islet transplant. Subjects may undergo up to 3 transplants in the course of this study; the final transplant can occur not later than 8 months following the first transplant.

In the first period, individuals who meet the general inclusion criteria will be approached regarding participation in the study. After informed consent has been obtained, they will be formally enrolled into the study. Eligibility will be confirmed based on the results of the screening visit procedure detailed in Appendix 1 of the CIT-07 protocol. Enrolled subjects who meet the eligibility screening for the studies will be put on the waiting list for an islet transplant.

Once a compatible islet preparation becomes available, a subject's eligibility will be re-confirmed and eligible subjects will begin immunosuppression therapy on Day -2 (Day 0 is defined as the day of transplant).

During the post-transplant follow-up period, subjects may receive up to two additional transplants. After receiving his/her initial islet transplant, if a subject does not meet the criteria for insulin independence described in Section 4.1.2 of the CIT-07 protocol, but has either a basal or stimulated C-peptide level ≥ 0.3 ng/mL (0.1 nmol/L), s/he will be considered for a second islet transplant. A second islet transplant will be considered at 75 ± 5 days after the first islet transplant and when all required metabolic assessments are complete. If, after the second islet transplant, both basal and stimulated C-peptide levels remain <0.3 ng/mL (0.1 nmol/L), the recipient will be considered to have failed the endpoint, and immunosuppression will be managed as described in the protocol. A third islet transplant will be considered only if all the criteria described in Section 7.4 of the CIT-07 protocol are met. Islet transplant recipients who have completed 12 months of follow up after their first infusion will no longer be eligible for additional islet transplants under the CIT-07 protocol.

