3.8.2.1 Analyses at 75±5 days following the initial and final infusion

At 75±5 days following the initial and final islet transplant (if applicable), the incidence rates for each type of AE, grouped by severity, will be reported. For each type of AE, the number of resolved events will be counted as well. The mean, median, standard deviation and range for the number of days until the AE is resolved will be calculated. The results will be summarized in the table provided in SAP Appendix 2. Moreover, we will also report AEs categorized by attribution that is, AEs related to the islet transplant procedure or to immunosuppression; the report format is shown in SAP Appendix 3.

For second and third islet transplants, immunosuppression is modified by using Daclizumab (Zenapax[®]) instead of Thymoglobulin[®] for induction. For subjects who receive more than one islet transplant, we will compare the incidence rate at 75±5 days following the initial and final islet transplant for all AEs related to the islet transplant procedure and to immunosuppression one at a time using the McNemar's matched-pair test [8]. The claim of a difference in incidence rate will be made if the p-value is less

than 0.05. If the incidence is rare in certain severity categories for an AE, we will compare the incidence rate regardless the severity to accommodate the validity of the test.

The incidence rate of immune sensitization, defined as detection of anti-HLA antibodies at 75 ± 5 days following the initial and final islet transplant, (if applicable) will be reported. The exact two-sided 95% confidence interval of the incidence rate will also be reported.

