3.8.2.2 Analyses at 365±14 days following the initial and final infusion

At 365±14 days following the initial and final islet transplant (if applicable), the incidence rates for each type of AE, grouped by severity, will be reported. For each type of AE, the number of resolved events will be counted as well. The mean, median, standard deviation and range for the number of days until the AE is resolved will be calculated. The results will be summarized in the table provided in Appendix 3. Moreover, we will also report the individuals who incur the AEs related to the islet transplant procedure and immunosuppression therapy, and the report is given in the table described in Appendix 3.

For subjects who require more than one islet transplant, we will compare the incidence rate at 365±14 days following the initial and final islet transplant for all the AEs related to the islet transplant procedure and immunosuppression therapy one at a time using the McNemar's matched-pair test [8]. The claim of difference in incidence rate will be made if the p-value is less than 0.05. If AE incidence is rare in certain severity categories, we will compare the incidence rate regardless of the severity to accommodate the validity of the test.

Adverse events may require a change in the immunosuppression for an individual transplant recipient. We will document the number and proportion of participants who require such a change.

For subjects who do not present the anti-HLA antibodies prior to transplantation, we will calculate the incidence rate of immune sensitization defined by detecting anti-HLA antibodies at 365±14 days following the initial and final islet transplant, (if applicable). The exact two-sided 95% confidence interval of the incidence rate will also be reported.

At 365±14 days following the initial islet transplant, we will also assess the change in retinal photography from pre-transplant. The incidence rate of worsening retinopathy will be calculated and the exact two-sided 95% confidence interval of the rate will be provided.

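### Three secondary analyses use ill-defined windows or denominators: the Day-365 McNemar test compares overlapping periods, Day-75 anti-HLA incidence includes pre-existing antibodies, and the Day-75 HYPO score has two conflicting look-back periods

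*SAP*

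**What the plan says.** **Day-365 McNemar test.** SAP 3.8.2.2 states: "For subjects who require more than one islet transplant, we will compare the incidence" of each related adverse event at 365±14 days after the initial and after the final transplant. Event types are tested one at a time, and a difference is claimed at p<0.05. SAP 3.1.1 allows a second transplant from 75±5 days after the first and adds that "the final transplant can occur not later than 8 months following the first transplant". SAP 3.8.2.1, which plans the same test at Day 75, introduces it by noting that later transplants use a different induction agent.

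**Anti-HLA.** SAP 2.3.2.3, under a heading that covers both Day 75 and Day 365, defines immune sensitization by "antibodies absent prior to transplantation". SAP 3.8.2.2 restricts the Day-365 rate to subjects without such antibodies before transplant. SAP 3.8.2.1 has no such restriction: "The incidence rate of immune sensitization, defined as detection of anti-HLA antibodies at 75" ± 5 days.

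**HYPO score.** SAP 3.7.5.6 says the score involves a four-week record together with "recall of all severe hypoglycemic episodes in the previous 12 months". The next sentence says it is "based on the severity of hypoglycemic events over a four week period". On timing: "The HYPO score will be measured at 75 ± 5 days following the initial and final infusion". Change from baseline and the proportion scoring 1047 or more are then analysed.

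**The concern.** The McNemar test is meant to contrast one transplant and its immunosuppression with another in the same subject. If the year counted for the first transplant also contains the final procedure and its induction, the two members of each pair are not separate observations, yet a formal claim of difference hangs on the result.

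For anti-HLA, a persisting pre-transplant antibody would be reported as new sensitization at Day 75 and excluded at Day 365. The two rates of one named safety endpoint would then not be comparable.

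For HYPO, if the 12-month recall applies, a score taken 75 days after transplant mostly describes the pre-transplant period, in subjects whose history of severe episodes is part of the target population (SAP 2.2.1). Any improvement would be understated. If the four-week period applies, there is no such problem. The SAP does not say which holds.

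**Working it through.** The SAP gives no figure for any of these quantities, so there is nothing to reproduce first.

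**1. McNemar windows**

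Inputs: nominal 365-day windows (3.8.2.2), and final transplant on day F after the first, from F = 70 (75 − 5) to F = 243 (8 months) (3.1.1).

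The windows are [0, 365] and [F, F + 365], so the overlap is 365 − F.

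| F | Shared days | Share of 365 |
|---|---|---|
| 70 | 295 | 81% |
| 75 | 290 | 79% |
| 180 | 185 | 51% |
| 243 | 122 | 33% |

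For the Day-75 comparison, the overlap is at most 80 − 70 = 10 days (second transplant at Day 70, assessment at Day 80).

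*Events spread evenly over time (simulation).* Assumptions: 24 re-transplanted subjects, constant hazards equivalent to 365-day risks of 60% after the first and 20% after the final transplant, exact two-sided test.

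| Windows | Mean discordant pairs | Power |
|---|---|---|
| Separate | about 13.4 | about 0.72 |
| Planned, F = 75 | 4.0 | 0.06 |
| Planned, F = 150 | 7.3 | 0.27 |
| Planned, F = 240 | 10.4 | 0.50 |

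With equal risks of 30%, the planned windows reject in 0.1 to 1.5% of simulations. For this type of event the overlap costs power and creates no false positives.

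*Events clustered at the infusion*, such as bleeding or biliary puncture (listed in 3.8.2). Assumptions: 24 subjects with two transplants each, the same independent risk r at each procedure, events only near the infusion.

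- An event at the final infusion falls in both windows, so final-only pairs cannot occur.
- An initial-only pair needs an event at the first infusion and none at the final: probability r(1 − r).
- With k discordant pairs all in one direction, p = 2 × 0.5^k. This is 0.0625 at k = 5 and 0.031 at k = 6, so rejection needs k ≥ 6.
- False rejection is therefore P(Binomial(24, r(1 − r)) ≥ 6).

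| r | r(1 − r) | False rejection |
|---|---|---|
| 10% | 0.09 | 2% |
| 20% | 0.16 | 17% |
| 30% | 0.21 | 39% |

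Every such rejection shows the first transplant as worse, although the two procedures carry equal risk.

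**2. Anti-HLA at Day 75**

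Let q be the share positive before transplant, with antibodies that persist, and s the true rate of new sensitization among the rest. The rate reported under 3.8.2.1 is q + (1 − q)s. The SAP gives neither value; those below are assumptions.

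| q | s | Reported |
|---|---|---|
| 0 | 5% | 5% |
| 10% | 0 | 10% |
| 10% | 5% | 14.5% |
| 20% | 5% | 24% |

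Restricting to subjects negative beforehand removes q, and the reported rate becomes s.

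**3. HYPO at Day 75**

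- 12-month recall: 365 − 75 = 290 pre-transplant days, 290/365 = 79% (78% at Day 80, 81% at Day 70).
- 75 days after a final transplant on day F, the recall reaches 365 − (F + 75) days before the first transplant: 215 days at F = 75, 47 days at F = 243.
- Four-week period: about Day 47 to Day 75, with no pre-transplant days.
- At Day 365±14, even 12-month recall reaches back at most 14 days before transplant.

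**The case against.** A reader might infer that all three are before/after measures that count the same events on both sides and so cannot show any change. The documents do not support that. The McNemar test compares two post-transplant windows, and discordant pairs can still reveal a difference: power is 0.50 at F = 240 in the illustration. The anti-HLA result is a single proportion with nothing counted twice. The HYPO problem exists only under one of two conflicting sentences, and even then the four-week record is wholly post-transplant, so change is diluted, not erased. Moreover, 79% is a share of days, not of the score, and the SAP does not give the weight of the recalled episodes within it.

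Nor would a Day-75 hypoglycemia benefit be hidden. Continuous glucose monitoring at Day 75 gives the number and duration of episodes from a 72-hour period (3.7.5.11), severe events are counted from Day 28 (2.3.1), and HYPO is repeated at Day 365 (3.7.6.6).

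On anti-HLA, it can fairly be said that the definition in 2.3.2.3 already governs Day 75 and that 3.8.2.1 is only loosely worded. That makes it an inconsistency to align, but the analysis section is what a programmer would follow. Any error needs subjects who were positive before transplant, and the SAP does not show that there were any.

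The argument that overlap merely makes pairs concordant, and is therefore conservative, holds for events spread over time. It fails for events tied to the infusion. It is also true that a nearly clean Day-75 McNemar comparison is already planned and that 3.7.2 calls the secondary analyses descriptive. Even so, 3.8.2.2 attaches a claim of difference to p<0.05.

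**Conclusion.** The McNemar and anti-HLA points stand on the SAP's own text; the HYPO point stands as an internal contradiction.

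- **McNemar, Day 365.** An overlap of 33 to 81% follows directly from 3.1.1, given the 8-month limit, which 3.7.5 also uses. The direction of the error depends on event timing: loss of power for events spread over time, false evidence against the first transplant for events at the infusion. The power and false-rejection figures are illustrative. They assume 24 re-transplanted subjects and the risks shown, none of which the SAP gives.
- **Anti-HLA, Day 75.** The rate is misdefined against 2.3.2.3 and 3.8.2.2. The overstatement is zero if nobody was positive beforehand and can approach the share that was.
- **HYPO, Day 75.** The look-back is not fixed. It contains 79% pre-transplant days under one sentence and none under the other.

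All three are secondary or safety analyses, and the primary endpoint is unaffected. They should be corrected, but they do not threaten the main conclusion.

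**What to change.** 1. **3.8.2.2:** drop the Day-365 McNemar test, or replace it with event rates in non-overlapping intervals (first to final transplant, then after the final transplant). Rely on the Day-75 comparison for the paired contrast, and state how an event in its overlap of up to 10 days is assigned.
2. **3.8.2.1:** restrict the Day-75 sensitization rate, numerator and denominator, to subjects antibody-negative before the first transplant, as 3.8.2.2 does.
3. **3.7.5.6:** reconcile the 12-month and four-week sentences, and state that the Day-75 score uses only post-transplant events.

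The cost is SAP wording and derivation changes on data already collected, with no new assessments and no effect on sample size.

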3.7.5.9 C-peptide/(glucose·creatinine) ratio

This measure accounts for both the dependence of C-peptide secretion on the ambient glucose concentration and the dependence of C-peptide clearance on kidney function [10, 11]. This ratio is a continuous variable and will be measured at 75 ± 5 days following the initial and final infusion (if applicable). The analysis of this variable adopts the method for a continuous variable.

3.7.5.10 Acute insulin response to glucose (AIR_{glu}), insulin sensitivity, and disposition index derived from the insulin-modified frequently-sampled intravenous glucose tolerance (FSIGT) test

The insulin modified FSIGT test will be performed at 75 ± 5 days following the initial and final infusion (if applicable). AIR_{glu} , SI and DI, derived from the test, provide a composite measure of β -cell function. AIR_{glu} is calculated as the incremental area-under-the-curve for insulin between 0 and 10 minutes post injection. SI, a measure of insulin-

dependent glucose disposal, is derived from Bergman's minimal model using MinMod Millennium software. The DI is calculated by $AIR_{glu} * SI$. The three variables are all continuous and analyzed using the method for a continuous variable.

3.7.5.11 Glucose variability and hypoglycemia duration derived from the continuous glucose monitoring system (CGMS)

CGMS involves the subcutaneous placement of a glucose sensor connected by tubing to a pager-sized monitoring device that stores glucose data obtained every 5 minutes over a 72-hour period. Data from a 72-hour period at 75 ± 5 days following the initial and final infusion (if applicable) will be used to derive the glucose variability and hypoglycemia duration.

The glucose variability is the absolute value of measured glucose minus 5.5 mmol/L [100mg/dL] and is a continuous variable. This variable will be analyzed using the method for a continuous variable. The data from the 72-hour period are used to derive the number and duration of all hypoglycemic episodes (measured glucose < 3.0 mmol/L [54 mg/dL]). Then the total duration of hypoglycemia can be calculated. The hypoglycemia duration is a continuous variable and is analyzed using the method for a continuous variable. The distribution of the number of hypoglycemic events will be tabled.

